11.3.3. Reporting Standards for Pharmacokinetic

Pharmacokinetic Concentration Data	
PC Windows Non-Linear (WNL) File	PC WNL file (CSV format) for the non compartmental analysis by Clinical Pharmacology Modelling and Simulation function will be created according to PK IDSL Standards. Note: Concentration values will be imputed as per GUI_51487
Descriptive Summary Statistics, Graphical Displays and Listings	Refer to IDSL PK Display Standards. Refer to IDSL Statistical Principle 6.06.1. Note: Concentration values will be imputed as per GUI_51487 for descriptive summary statistics and summarized graphical displays only. The number of values imputed will be included as a column in the summary tables.
NONMEM/Pop PK File	Not applicable.
NONMEM/PK/PD File	Not applicable.
Pharmacokinetic Parameter Derivation	
PK Parameters to be Derived by Programmer	None
Pharmacokinetic Parameter Data	
Is the 'NQ impacted PK Parameters' Rule Being Followed?	Yes, refer to Standards for Handling NQ Impacted PK Parameters.
Descriptive Summary Statistics, Graphical Displays and Listings	Refer to IDSL PK Display Standards.

11.4. Appendix 4: Derived and Transformed Data

11.4.1. General

Multiple Measurements at One Analysis Time Point

- The mean of the measurements will be calculated and used in any derivation of summary statistics but if listed, all data will be presented.
- Participants having both High and Low values for Normal Ranges at any post-baseline visit for safety parameters will be counted in both the High and Low categories of “Any visit post-baseline” row of related summary tables. This will also be applicable to relevant Potential Clinical Importance summary tables.

Study Day

- Calculated as the number of days from First Dose Date within the period in question (in period 1 this will be the date of dosing with nemiralisib; in period 2 this will be the date of first dosing with itraconazole):
 - Ref Date = Missing → Study Day = Missing
 - Ref Date < First Dose Date → Study Day = Ref Date – First Dose Date
 - Ref Date ≥ First Dose Date → Study Day = Ref Date – (First Dose Date) + 1

11.4.2. Study Population

Demographics

Age

- GSK standard algorithms will be used for calculating age where birth date is imputed as:
 - Any subject with a missing day will have this imputed as day '15'.
 - Any subject with a missing date and month will have this imputed as '30th June'.
 - Birth date will be presented in listings as 'YYYY'.

Body Mass Index (BMI)

- Calculated as Weight (kg) / [Height (m)]²

Extent of Exposure

- Number of days of exposure to each study drug will be calculated for each period based on the formula:
Duration of Exposure in Days = Treatment Stop Date – (Treatment Start Date) + 1
- Participants who were assigned treatment but did not report a treatment start date will be categorised as having zero days of exposure.
- The cumulative dose will be based on the formula:
Cumulative Dose = Sum of (Number of Days x Total Daily Dose)
- If there are any treatment breaks during the study, exposure data will be adjusted accordingly.

11.4.3. Safety

Adverse Events
AE Time Since First Dose (Days)

• If AE start date/time < date/time of first dose then Time since first dose = date of first dose – AE start date• If AE start date/time \geq date/time of first dose then Time since first dose = AE start date – date of first dose+1• Missing if AE start date or date of first dose is missing.• Note: First dose will be the date of dosing with nemralisib in period 1 and the date of first dosing with itraconazole in period 2.
AE Duration (Days)

• AE end date – AE start date + 1• Missing if AE start date or end date is missing.
AE's of Special Interest

• Post-inhalation cough is an AE of special interest. The lower level term (LLT) to be included is "coughing after drug inhalation"

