### 3.3.1. Risk Assessment

Potential Risk of Clinical Significance	Summary of Data/Rationale for Risk	Mitigation Strategy
Investigational Product (IP)		
Bronchospasm	Can potentially occur with any inhaled treatment.	
All doses of study treatment will be administered in the clinical pharmacology unit in the presence of trained clinical staff.
 
Treatment with a short-acting inhaled bronchodilator will be available and administered as appropriate and determined by the Investigator. Participants will receive no more nemiralisib treatment and may be withdrawn from the study.

Mucosal irritancy	Detected in 13 week toxicology study in the dog.	Participants will be regularly monitored for AEs. No evidence of mucosal irritancy has been seen so far in clinical studies.
Itraconazole administration	
The most common Adverse Drug Reactions associated with the administration of itraconazole are:
 
 
- Upper respiratory tract infections
 
- Increased hepatic enzymes
 
- Hypoacusis
 
- Headache
 
- Abdominal pain
 
- Diarrhea
 
	
Only healthy participants will be allowed to participate in the proposed study.
 
Exclusion criteria, close monitoring of clinical parameters and adverse events will be conducted. Stopping criteria will be utilised to mitigate and assess cardiovascular and liver effects.

Potential Risk of Clinical Significance	Summary of Data/Rationale for Risk	Mitigation Strategy
	

- Nausea

- Fatigue

- Arrhythmia

- Cough

- Sore throat

- Back pain

 
Refer to the FDA label (Itraconazole Prescribing Information, 2010) for itraconazole for the full list of Adverse Drug Reactions.
	

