### **9.2.2. Method of Detecting AEs and SAEs**

Care will be taken not to introduce bias when detecting AE and/or SAE. Open-ended and non-leading verbal questioning of the participant is the preferred method to inquire about AE occurrence.

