## Recording AE and SAE

### AE and SAE Recording

- When an AE/SAE occurs, it is the responsibility of the investigator to review all documentation (eg, hospital progress notes, laboratory, and diagnostics reports) related to the event.
- The investigator will then record all relevant AE/SAE information in the CRF.
- It is **not** acceptable for the investigator to send photocopies of the participant's medical records to GSK in lieu of completion of the GSK /AE/SAE CRF page.
- There may be instances when copies of medical records for certain cases are requested by GSK. In this case, all participant identifiers, with the exception of the participant number, will be redacted on the copies of the medical records before submission to GSK.
- The investigator will attempt to establish a diagnosis of the event based on signs, symptoms, and/or other clinical information. Whenever possible, the diagnosis (not the individual signs/symptoms) will be documented as the AE/SAE.

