8.2. Adverse Events of Special Interest Analyses

Post-inhalation cough immediately following dosing is an adverse event of special interest (AESI). This will be captured if a participant reports it as an AE. The details of the planned displays are provided in [Appendix 8: List of Data Displays](#).

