11.2.2. Treatment Emergent Flag for Adverse Events

Flag	Definition
Treatment Emergent	
 • If AE onset date is on or after study treatment start date (for that period) & on or before nemiralisib treatment stop date (for that period) plus 10 days (5 times half life of nemiralisib). • Study Treatment Start Date (for that period) \leq AE Start Date \leq Nemiralisib Treatment Stop Date (for that period) + 10 days . • Where 'study treatment' start date (for that period) refers to the date of the first dose given in that period (i.e. nemiralisib for period 1 and itraconazole for period 2)

NOTES:

- If the study treatment stop date is missing, then the AE will be considered to be On-Treatment.
- Time of study treatment dosing and start/stop time of AEs should be considered, if collected.

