16.	Safety	AE9CPA	Listing of Serious Adverse Events	ICH E3 Drop 'Maximum Grade' variable Add Footnote: 'Nemiralisib was administered on Day 1 of Period 1 and Day 5 of Period 2.'	SAC
17.	Safety	AE14	Listing of Reasons for Considering as a Serious Adverse Event	ICH E3	SAC
18.	Safety	AE9CP	Listing of Adverse Events Leading to Withdrawal from Study / Permanent Discontinuation of Study Treatment	ICH E3 Drop 'Maximum Grade' variable Add Footnote: 'Nemiralisib was administered on Day 1 of Period 1 and Day 5 of Period 2.'	SAC
Adverse Events of Special Interest					
19.	Safety	AE9CP	Listing of Adverse Events Categorised as Post Inhalation Cough	Drop 'Maximum Grade' variable Add Footnote: 'Nemiralisib was administered on Day 1 of Period 1 and Day 5 of Period 2.'	SAC
Hepatobiliary (Liver)					
20.	Safety	MH2	Listing of Medical Conditions for Participants with Liver Stopping Events	IDSL	SAC
21.	Safety	SU2	Listing of Substance Use for Participants with Liver Stopping Events	IDSL	SAC

ICH: Listings					
No.	Population	IDSL / Example Shell	Title	Programming Notes	Deliverable [Priority]
All Laboratory					
22.	Safety	LB6	Listing of All Chemistry Data for Participants with Any Value of Potential Clinical Importance	ICH E3 Add Footnote: 'Nemiralisib was administered on Day 1 of Period 1 and Day 5 of Period 2.'	SAC
23.	Safety	LB6	Listing of All Hematology Data for Participants with Any Value of Potential Clinical Importance	ICH E3 Add Footnote: 'Nemiralisib was administered on Day 1 of Period 1 and Day 5 of Period 2.'	SAC
24.	Safety	LB6	Listing of Chemistry Values of Potential Clinical Importance	Add Footnote: 'Nemiralisib was administered on Day 1 of Period 1 and Day 5 of Period 2.'	SAC
25.	Safety	LB6	Listing of Hematology Values of Potential Clinical Importance	Add Footnote: 'Nemiralisib was administered on Day 1 of Period 1 and Day 5 of Period 2.'	SAC
26.	Safety	LB14	Listing of Laboratory Data with Character Results	ICH E3 Include Treatment/Period and sort as for a crossover study. Add Footnote: 'Nemiralisib was administered on Day 1 of Period 1 and Day 5 of Period 2.'	SAC
ECG					
27.	Safety	EG4	Listing of All ECG Values for Participants with Any Value of Potential Clinical Importance	IDSL Include actual relative time. Add Footnote: 'Nemiralisib was administered on Day 1 of Period 1 and Day 5 of Period 2.'	SAC

ICH: Listings					
No.	Population	IDSL / Example Shell	Title	Programming Notes	Deliverable [Priority]

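### Listing 19 may miss a cough that meets the SAP's own definition of the adverse event of special interest, because selection rests on one coded term with no onset time

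*SAP*

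**What the plan says.** SAP 8.2 sets the definition: "Post-inhalation cough immediately following dosing is an adverse event of special interest (AESI". It relies on ordinary AE reporting: "This will be captured if a participant reports it as an AE". No length of time is attached to the word immediately.

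SAP 11.4.3 turns this into a selection rule: "The lower level term (LLT) to be included is 'coughing after drug inhalation". The result is shown in one place, Listing 19 in SAP 11.8.8, titled "Listing of Adverse Events Categorised as Post Inhalation Cough". The safety tables in SAP 11.8.7 contain no AESI summary.

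On how AEs are obtained, Protocol 9.2.2 says: "Open-ended and non-leading verbal questioning of the participant is the preferred method to inquire about AE occurrence". Protocol Appendix 4 adds: "Whenever possible, the diagnosis (not the individual signs/symptoms) will be documented as the AE/SAE". The protocol does not mention this AESI and does not tell staff how to word a cough that follows inhalation.

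On timing, Protocol 7.6 has the date and time of every dose recorded. AE times are less certain. SAP 11.2.2 says, for the treatment-emergent flag only: "Time of study treatment dosing and start/stop time of AEs should be considered, if collected".

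**The concern.** The definition depends on when the cough happens. The rule depends on the words written down and how they are coded. The two agree only if every cough right after inhalation is recorded in a way that codes to the named lower level term (LLT). Nothing in either document ensures this: there is no prompt, no wording instruction and no planned review of cough events.

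At stake is whether Listing 19 is complete. The sponsor singled this event out, and a reader of the study report will take that listing as the account of it. A short or empty listing could mean that few such coughs occurred, or that they were recorded as plain cough.

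**Working it through.** The plan states no figure on this point, so there is nothing to reproduce. The check sets the passages side by side.

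**1. Definition against rule**

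| Cough | Coded to the named LLT | Coded to another cough term |
|---|---|---|
| Immediately after inhalation (meets SAP 8.2) | in Listing 19 | **not in Listing 19** |
| At another time (does not meet SAP 8.2) | in Listing 19 | not in Listing 19 |

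The bold cell is the gap: the event satisfies 8.2, but 11.4.3 does not select it.

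**2. Does anything else route that event to Listing 19?** Neither document contains a second term, an onset window, a CRF field for cough on inhalation or a medical review step.

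**3. Does the derived onset variable recover it?** SAP 11.4.3 derives time since first dose in whole days, as AE start date − date of first dose + 1 for an AE on or after that dose. In Period 2 the first dose is itraconazole on Day 1.

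- Period 1, Day 1: 1 − 1 + 1 = 1
- Period 2, Day 5: 5 − 1 + 1 = 5

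On Period 2 Day 5 the value is 5 for a cough before any dose that morning, in the hour between itraconazole and nemiralisib, just after inhalation, or in the evening. The variable cannot identify immediate cough. The footnote on Listings 13 and 19 adds only the nemiralisib dosing day.

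**4. Where does the missed event remain visible?** It is counted in Table 3.1, which covers all AEs, and shown in Listings 13 and 14. Listing 15 links the recorded wording to the coded terms. None of these carries a specified criterion for onset after inhalation. SAP 5.1 defines only two treatment descriptors, and SAP 11.2.2 starts Period 2 emergence at the first itraconazole dose. On that basis a cough on Period 2 Days 1 to 4, before any inhalation in that period, would fall under the combination descriptor. Cough is on the protocol's itraconazole list in 3.3.1, introduced by "The most common Adverse Drug Reactions associated with the administration of itraconazole are".

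**5. Size.** Let s be the share of true post-inhalation coughs that are coded to the named LLT. Listing 19 shows s of them and misses 1 − s. The documents give no value for s, so the shortfall runs from 0 (s = 1) to all of them (s = 0). For scale, about 20 participants × 2 inhalations = about 40 inhalations, so one missed event is 1/40 = 2.5% of inhalations.

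**The case against.** The other side has a strong case on consequence.

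- **The under-count is not shown.** A reader might infer that Listing 19 will under-report. The documents do not support this, because they do not show how such a cough would be worded or coded. CRF guidance, coding conventions and display specifications lie outside them and could close the gap. This stands: the listing may miss events, and no more can be said.
- **No safety data are lost.** A reader might infer that an unlisted cough disappears. It does not; it stays in Table 3.1 and Listings 13 to 15. This stands.
- **No comparison is distorted.** A reader might infer that nemiralisib alone and nemiralisib with itraconazole would be wrongly compared on this event. No AESI summary by treatment, test or decision rule is planned. The study has one centre, with supervised dosing in both periods, so wording is less likely to differ between treatments. This stands.
- **The recording instructions do not favour plain cough.** Preferring a diagnosis to a symptom could equally lead to the more specific term, and open questioning does not stop staff from linking a cough to a dose they have just supervised. This stands; these passages show only that the specific wording is not prompted.
- **A specific term protects against itraconazole cough.** This stands in part. It argues against adding every cough term without a timing condition. It does not justify a rule with no timing condition for an event defined by timing.

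What remains is the mismatch itself: SAP 11.4.3 does not implement SAP 8.2, and no derivation specified in the SAP makes up for it.

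**Conclusion.** The point holds as a minor one. As written, a cough that meets the SAP 8.2 definition but is not coded to the named LLT is left out of the only AESI display. The size cannot be estimated from the documents. The effect is confined to membership of one descriptive listing; the primary pharmacokinetic analysis and the overall AE reporting are untouched.

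This rests on two assumptions: that Listing 19 is programmed from SAP 11.4.3 as it stands, and that no guidance outside the two documents fixes how such coughs are worded or coded. If such guidance exists and is followed, the gap may be empty in practice, and citing it in the SAP would largely settle the matter.

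**What to change.** In SAP 11.4.3, before database freeze:

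1. Keep the named LLT.
2. Also select any AE coded to a cough term with onset on the nemiralisib dosing day (Period 1 Day 1, Period 2 Day 5), at or after inhalation. List the cough terms explicitly, since the coding dictionary is not part of the documents.
3. Show onset time relative to inhalation in Listing 19.
4. Flag onsets within a short window that the sponsor pre-specifies to represent *immediately* in SAP 8.2.

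Steps 3 and 4 are needed because the dosing-day condition alone is too wide. On Period 2 Day 5 itraconazole is given one hour before nemiralisib, so a same-day cough need not be due to inhalation.

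The cost is a few lines of SAP text and some programming, plus one data requirement. Nemiralisib dose times are already recorded, but AE start time must be collected for cough on the two dosing days, and the SAP does not guarantee this at present. A few same-day coughs unrelated to inhalation may also be listed, including possible itraconazole cough on Period 2 Day 5; their times would be visible.

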11.5. Appendix 5: Reporting Standards for Missing Data

11.5.1. Premature Withdrawals

Element	Reporting Detail
General	
 Subject study completion (i.e. as specified in the protocol) was defined as completing all phases of the study including the last visit. Withdrawn subjects may be replaced in the study. All available data from participants who were withdrawn from the study will be listed and all available planned data will be included in summary tables and figures, unless otherwise specified.

11.5.2. Handling of Missing Data

Element	Reporting Detail
General	
 Missing data occurs when any requested data is not provided, leading to blank fields on the collection instrument: 
 These data will be indicated by the use of a “blank” in subject listing displays. Unless all data for a specific visit are missing in which case the data is excluded from the output. Answers such as “Not applicable” and “Not evaluable” are not considered to be missing data and should be displayed as such. Data below the limit of quantification (BLQ) is not missing data and must be displayed as ‘NQ (< x)’ where x is the lower limit of quantification, and included in all listings and summaries. Analysis will be performed on all available data and no imputation will be performed for missing data.
Outliers	
 Any participants excluded from the summaries and/or statistical analyses because their values are considered outliers will be documented along with the reason for exclusion in the clinical study report.

11.5.2.1. Handling of Missing and Partial Dates

Element	Reporting Detail
General	
 Partial dates will be displayed as captured in subject listing displays.
Adverse Events	
 The eCRF allows for the possibility of partial dates (i.e., only month and year) to be recorded for AE start and end dates; that is, the day of the month may be missing. In such a case, the following conventions will be applied for calculating the time to onset and the duration of the event: 
 Missing Start Day: First of the month will be used unless this is before the start date of study treatment; in this case the study treatment start date will be used and hence the event is considered On-treatment as per Appendix 2: Study Phases and Treatment Emergent Adverse Events. Missing Stop Day: Last day of the month will be used, unless this is after the stop date of study treatment; in this case the study treatment stop date will be used. Note: start date and stop dates are defined as the first/last dose given in the period, regardless of whether it is nemralisib or itraconazole. Completely missing start or end dates will remain missing, with no imputation applied.

Element	Reporting Detail
	Consequently, time to onset and duration of such events will be missing.
Concomitant Medications/ Medical History	
Partial dates for any concomitant medications recorded in the CRF will be imputed using the following convention:
If the partial date is a start date, a '01' will be used for the day and 'Jan' will be used for the monthIf the partial date is a stop date, a '28/29/30/31' will be used for the day (dependent on the month and year) and 'Dec' will be used for the month.The recorded partial date will be displayed in listings.

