### **9.2.1. Time Period and Frequency for Collecting AE and SAE Information**

- All SAEs will be collected from the signing of the ICF until the follow-up visit at the time points specified in the SoA (Section 2).
- All AEs will be collected from the start of treatment until the follow-up visit at the time points specified in the SoA (Section 2).
- Medical occurrences that begin before the start of study treatment but after obtaining informed consent will be recorded on the Medical History/Current Medical Conditions section of the case report form (CRF) not the AE section.
- All SAEs will be recorded and reported to the sponsor or designee immediately and under no circumstance should this exceed 24 hours, as indicated in [Appendix 4](#). The investigator will submit any updated SAE data to the sponsor within 24 hours of it being available.
- Investigators are not obligated to actively seek AEs or SAEs in former study participants. However, if the investigator learns of any SAE, including a death, at any time after a participant has been discharged from the study, and he/she considers the event to be reasonably related to the study treatment or study participation, the investigator must promptly notify the sponsor.

- The method of recording, evaluating, and assessing causality of AEs and SAEs and the procedures for completing and transmitting SAE reports are provided in [Appendix 4](#).

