2.3. Study Design

Overview of Study Design and Key Features	
Design Features	
 One sequence crossover, open label, single centre. There will be a washout of at least 14 days between the administration of nemiralisib in Period 1 and the administration of nemiralisib in Period 2. Subjects will be admitted to the clinical research unit on Day -1 and will remain in-house until collection of the final PK sample in each period. The final PK sample will be Day 6 in Period 1 and Day 11 in Period 2.
Dosing	
 Period 1, nemiralisib: On Day 1, subjects will receive a single dose of 100 mcg nemiralisib. Period 2, itraconazole: From Day 1 to 10 inclusive, subjects will receive a single dose of 200 mg itraconazole in the morning Period 2, nemiralisib: On Day 5, subjects will receive a single dose of 100 mcg nemiralisib one hour after the dose of 200 mg itraconazole. Participants will receive the administration of nemiralisib on Day 5 and itraconazole doses on Day 5 to Day 10 only if there are no findings that are considered clinically significant by the Investigator (in consultation with the medical monitor if needed) during review of Day 4 clinical chemistry and ECG.
Time & Events	
 Refer to Appendix 1: Schedule of Activities.
Treatment Assignment	
 All subjects will receive the same treatments in the same periods/on the same study days.
Interim Analysis	
 A preliminary assessment of PK will be performed following the availability of the PK data, for internal decision making.

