5. CONSIDERATIONS FOR DATA ANALYSES AND DATA HANDLING CONVENTIONS

5.1. Study Treatment & Sub-group Display Descriptors

Treatment Group Descriptions	
Data Displays for Reporting	
Description	Order in TLF
NEMI 100mcg SD Alone	1
NEMI 100mcg SD with Itraconazole 200mg RD	2

Treatment comparisons will be displayed using the descriptors as follows:

- NEMI 100mcg SD with Itraconazole 200mg RD vs. NEMI 100mcg SD Alone

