Brief physical examination	X											X	
Laboratory assessments (hematology, clinical chemistry and urinalysis)	X										X		Pre-dose at all timepoints. Day -1 results to be reviewed before dosing on Day 1.
Clinical chemistry only			X		X		X		X				Pre-dose at all timepoints. Day 4 results to be reviewed before itraconazole dosing on Day 5.
12-lead ECG		X	X		X		X		X		X		Single measurement. Pre-dose and 3h post-dose (itraconazole) on Day 1. Pre-dose at all other timepoints, Day 4 results to be reviewed before itraconazole dosing on Day 5.
Vital signs		X	X		X		X		X		X		Single measurement. Pre-dose at all timepoints
Study treatment (itraconazole)		X	X	X	X	X	X	X	X	X			Approx. 1 h post standard meal.
FEV ₁					X								Triuplicate
Inhaler (Ellipta) training					X								Training conducted by reviewing the Patient Information Leaflet with the participant. Additional training may be conducted at the discretion of the investigator.
Study treatment (nemralisib)						X							1 h post itraconazole administration.
PK (nemralisib)						X	X	X	X	X	X	X	pre-dose, and 5 min, 30 min, 2 h, 6 h, 12 h, 24 h, 48 h, 72 h, 96 h, 120 h and 144 h post-dose (nemralisib)

Procedure	Treatment Period Days											Notes
	-1	1	2	3	4	5	6	7	8	9	10	
PK (itraconazole + hydroxy-itraconazole)		X				X	X					Pre-dose, 30 min, 1 h, 1.5 h, 2 h, 3 h, 4 h, 6 h, 8 h, 12 h post-dose (itraconazole) on Day 1 Pre-dose, 30 min, 1 h, 1.5 h, 2 h, 3 h, 4 h, 6 h, 8 h, 12 h and 24 h hours post-dose (itraconazole) on Day 5
AE review		←=====→										
SAE review	X	←=====→										
Concomitant medication review	X	←=====→										

- The timing and number of planned study assessments, including safety and pharmacokinetic assessments may be altered during the course of the study based on newly available data (e.g., to obtain data closer to the time of peak plasma concentrations) to ensure appropriate monitoring.
- Any changes in the timing or addition of time points for any planned study assessments must be documented and approved by the relevant study team member and then archived in the sponsor and site study files, but will not constitute a protocol amendment. The Institutional review board (IRB)/ Independent ethics committee (IEC) will be informed of any safety issues that require alteration of the safety monitoring scheme or amendment of the Informed consent form (ICF).

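### The missing-stop-day rule gives AE durations of zero or less when a dated onset follows the last dose, and AEs on Period 2 Days 1-4 have no itraconazole-alone label

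*SAP*

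**What the plan says.** **Stop dates.** SAP 11.5.2.1 sets conventions for partial AE dates, to be used in calculating time to onset and duration. A missing stop day becomes the last day of the month, "unless this is after the stop date of study treatment; in this case the study treatment stop date will be used". A note adds that "start date and stop dates are defined as the first/last dose given in the period, regardless of whether it is nemralisib or itraconazole". SAP 11.4.3 defines duration as "AE end date – AE start date + 1". Completely missing dates are not imputed. For listings, "Partial dates will be displayed as captured in subject listing displays".

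**Collection.** Protocol 9.2.1: "All AEs will be collected from the start of treatment until the follow-up visit". Follow-up is 5-10 days after the last itraconazole dose.

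**Dosing.** Period 1 has one nemiralisib dose, on Day 1. For Period 2, SAP 2.3 says "From Day 1 to 10 inclusive, subjects will receive a single dose of 200 mg itraconazole in the morning", with nemiralisib inhaled on Day 5.

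**Labels.** Protocol 10.3.2 has safety data summarised by treatment. SAP 5.1 defines two treatment descriptors, compared as "NEMI 100mcg SD with Itraconazole 200mg RD vs. NEMI 100mcg SD Alone". SAP 11.2.2 opens the Period 2 treatment-emergent window at the first itraconazole dose and closes it 10 days after the nemiralisib stop date. SAP section 4 analyses the Safety population by treatment actually received.

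**The concern.** The two parts are separate.

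1. AEs are collected well past the last dose, but an imputed stop date may not pass it. If onset is later than that limit, the event ends before it begins. Period 1 is the more exposed, because its only dose is on Day 1 and any onset from Day 2 is already beyond the limit. At stake is a derived variable that takes impossible values under a rule followed to the letter.

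2. Period 2 starts with four days of itraconazole only, inside the treatment-emergent window, yet neither label describes that exposure. The secondary safety objective concerns nemiralisib alone and with itraconazole. An event that starts on itraconazole before the inhalation, if counted under the combination, would read as an event of the combination. Protocol 3.3.1 lists cough and sore throat among the common itraconazole reactions, and both could be mistaken for effects of an inhaled drug.

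**Working it through.** **Part 1: duration**

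Inputs: the cap and its definition (SAP 11.5.2.1), the duration formula (SAP 11.4.3) and the last dose in each period (SAP 2.3). The plan gives no figure to reproduce.

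Let *d* be a known onset day and *L* the day of the last dose in the period. The stop date has a month and year but no day.

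- The event cannot end before it starts, so the last day of the stop month is on or after *d*.
- If *d* > *L*, that last day is also after *L*. The cap always applies and the imputed stop is *L*.
- Duration = *L* − *d* + 1, which is at most 0 when *d* > *L*.

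| Period | Last dose | Formula | Results |
|---|---|---|---|
| 1 | Day 1 | 2 − d | Day 1: 1; Day 2: 0; Day 3: −1; Day 6: −4; Day 11: −9 |
| 2 (text) | Day 10 | 11 − d | Day 1: 10; Day 11: 0; Day 12: −1; Day 15: −4 |
| 2 (grid as extracted) | Day 9 | 10 − d | Day 10: 0; Day 11: −1 |

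These onsets fall inside the plan's own windows. The treatment-emergent window runs to Day 1 + 10 = Day 11 in Period 1 and Day 5 + 10 = Day 15 in Period 2.

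An enumeration agrees. It used 365 possible Day 1 dates, 10 onset days after the last dose and 15 event lengths, giving 365 × 10 × 15 = 54,750 cases per period (Period 2 last dose on Day 10). All had a duration of 0 or less. No event starting on or before the last dose did.

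The cap also distorts valid-looking values. An event starting on the first dosing day with a missing stop day gets 1 day in Period 1 and up to 10 days in Period 2.

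Example, assuming Period 2 Day 1 is 5 March and the stop is recorded only as March:

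| Onset | SAP rule | Capped at follow-up on Day 15 | Capped at follow-up on Day 20 |
|---|---|---|---|
| Day 11 | 0 | 5 | 10 |
| Day 13 | −2 | 3 | 8 |
| Day 15 | −4 | 1 | 6 |

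**Part 2: labels**

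- Period 2 Days 1-4: itraconazole only (SAP 2.3), inside the treatment-emergent window (SAP 11.2.2). Neither SAP 5.1 label fits.
- Participants stopped before the Day 5 inhalation: foreseen by the Day 4 review in SAP 2.3 and by SAP 7.1.4. They take no Period 2 nemiralisib, so a window ending 10 days after it has no end date. A note in SAP 11.2.2 treats AEs as on-treatment when the study treatment stop date is missing. SAP 11.5.2.1 defines that date by the last dose of either drug, and these participants do have a last itraconazole dose. Whether the note covers them is unclear.
- Displays: six of the eight other safety tables (3.3, 3.4, 3.5, 3.8, 3.9 and 3.10) carry a footnote dating the nemiralisib doses. AE Tables 3.1 and 3.2 do not. AE Listing 13 does.

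Scale, on stated assumptions: if the tables count participants, each one whose only event of a given term began on Days 1-4 adds 1/20 = 5.0 percentage points to the combination column (1/16 = 6.3 with 16 participants). Days 1-4 are 4/15 = 27% of the Period 2 treatment-emergent window. Counting to follow-up (Days 15-20, or 14-19 if the last dose is on Day 9), they are between 4/20 = 20% and 4/14 = 29%. These are shares of days and do not predict the number of events.

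**The case against.** **On the stop-day rule.** A reader might infer that every event starting after the last dose with a missing stop day is affected. The SAP does not support that. A missing start day is set to the first of the month or, if that is too early, to treatment start. A true Period 1 Day 3 onset in the dosing month with both days missing becomes Day 1 to Day 1, a duration of 1. Completely missing stop dates stay missing. Nor does the rule corrupt AE counts or the treatment-emergent flag, which do not use the AE stop date. No planned safety table summarises duration, and partial dates are listed as captured. Participants are also in-house until Day 6 and Day 11, so missing stop days should mainly concern events ending after discharge. All of this stands and limits the consequence. It does not make the rule correct.

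**On the labels.** The SAP consistently treats Period 2 as one regimen starting with itraconazole: baseline, study day, time since first dose and the treatment-emergent start all use the first itraconazole dose. The second label can be read as naming that regimen, and there is no itraconazole-alone safety objective. A reader might therefore infer a breach of analysis by treatment received for all Day 1-4 events. That goes too far, because a participant who goes on to inhale on Day 5 did receive the combination. The conflict arises only for those stopped before Day 5, and Listing 4 shows their planned and actual treatment by period. The shells are available only on request (SAP 11.9), so the actual columns of Tables 3.1 and 3.2 cannot be seen. This stands and lowers confidence. It does not supply the missing assignment rule.

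**Conclusion.** Part 1 is wrong as written, with a small consequence. For an AE with a known onset after the last dose in the period and a stop date lacking only the day, duration is 0 or negative without exception. This starts at Day 2 in Period 1 and at Day 11 in Period 2 if the last dose is on Day 10. The damage is confined to derived duration.

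Part 2 is a cheap improvement, held with moderate confidence. On the SAP text, events starting on Period 2 Days 1-4 default to the combination label in Tables 3.1 and 3.2. For participants stopped before the inhalation, that also conflicts with analysis by treatment actually received. It rests on the assumption that the unseen shells add no itraconazole-only column. The listings let a reader separate the events by hand, so this is possible misattribution in two descriptive tables. No data are lost, and the primary pharmacokinetic analysis is untouched.

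Separately, the text gives itraconazole on Days 1-10, while the schedule grid as extracted marks Days 1-9. The extraction may be at fault. The passages must be reconciled, because the last dose sets the Period 2 cap.

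**What to change.** **SAP 11.5.2.1.** Impute the last day of the month, capped at the day before the first dose of the next period (Period 1), or at the follow-up visit or last contact (Period 2, or where there is no next period). The imputed date is never earlier than AE onset. This takes one sentence. An event that runs on from Period 1 into Period 2 with a missing stop day would be cut at the boundary, and the text should say that this is intended.

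**SAP 5.1 and Tables 3.1 and 3.2.** Assign each AE once, by onset:

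- nemiralisib alone: Period 1 dose to first itraconazole dose, or to follow-up if none is given;
- itraconazole alone: first itraconazole dose to the Day 5 inhalation, or to follow-up if no Period 2 nemiralisib is given;
- nemiralisib with itraconazole: inhalation to follow-up.

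Show itraconazole alone as its own column, with its own N and phase length. State how the treatment-emergent window ends for participants with no Period 2 nemiralisib dose.

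**Schedule.** Reconcile the itraconazole days in the grid with those in the text.

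**Cost.** SAP wording and one column in two tables, from data already collected. The phases are of unequal length, so crude percentages are not directly comparable. Itraconazole reactions starting after the inhalation stay with the combination. The AE tables would have one more column than the laboratory, ECG and vital-sign tables.
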